10.2 Clinical Laboratory Tests

Clinical laboratory tests for hematology, serum chemistry, and urinalysis will be summarized:

- Observed results at all analysis visits (Screening, Baseline, Week 2, Week 4, Follow-up, Last Post-Baseline Visit, Lowest Post-Baseline Result, Highest Post-Baseline Result, and Most Abnormal Post-Baseline Result)
 - o Descriptive statistics for numeric results
 - Most Abnormal Post-Baseline Result will be removed
 - o Frequency distributions for the categorical results
 - Lowest and Highest Post-Baseline Result will be removed
- Change from baseline for numeric results at all post-baseline analysis visits (Week 2, Week 4, Follow-up, Last Post-Baseline Visit, Lowest Post-Baseline Result, and Highest Post-Baseline Result)
- Shift tables for abnormalities from baseline to post-baseline visits
 - o Numeric Results: Low, Normal, and High
 - Shift tables will be presented by each post-baseline analysis visit, the overall lowest post-baseline result (scheduled or unscheduled), and the overall highest post-baseline result (scheduled or unscheduled).
 - o Categorical Results: Normal and Abnormal
 - Shift tables will be presented by each post-baseline analysis visit and the overall most abnormal post-baseline result (scheduled or unscheduled).

Hematology assessments will include total white blood cell count, differential (neutrophils, lymphocytes, monocytes, eosinophils, and basophils), hemoglobin, hematocrit, red blood cell count, platelet count, and HbA1c. HbA1c will be collected and analyzed at Screening (Visit 1) only.

Serum chemistry assessments will include electrolytes (bicarbonate, calcium, chloride, phosphorous, potassium, sodium, and magnesium), enzymes (alkaline phosphatase, aspartate aminotransferase, alanine aminotransferase, lactate dehydrogenase, and gamma-glutamyl transferase), and other (albumin, total bilirubin, direct bilirubin, indirect bilirubin, creatinine, calculated creatinine clearance (Cockcroft-Gault formula), glucose, triglycerides, total protein, blood urea nitrogen, and uric acid). Calculated creatinine clearance and triglycerides will be collected/calculated and analyzed at Screening (Visit 1) only. Only serum chemistry tests at Week 2 and the follow-up visits are planned to be collected and analyzed for these 6 liver function tests (alkaline phosphatase, aspartate aminotransferase, alanine aminotransferase, total bilirubin, direct bilirubin, and indirect bilirubin). No fasting for these liver function serum chemistry tests will be required, as is required for glucose and triglycerides.

Urinalysis will include pH, specific gravity, glucose, ketones, protein, blood, leukocyte esterase, urobilinogen, nitrites, and reflex microscopy.

Other clinical laboratory tests for hematology, serum chemistry, and urinalysis collected that are not stated above will be included in subject listings, but not in the summary tables.

Potentially Clinically Significant (PCS) Clinical Laboratory Tests:

Clinical Laboratory Category	Clinical Laboratory Test	PCS Threshold
Serum Chemistry	Alkaline Phosphatase (ALP)	> 2 x ULN
Serum Chemistry	Alanine Aminotransferase (ALT)	> 3 x ULN
Serum Chemistry	Aspartate Aminotransferase (AST)	> 3 x ULN
Serum Chemistry	Blood Urea Nitrogen (BUN)	> 1.5 x ULN
Serum Chemistry	Creatinine	>1.5 x Baseline or > 1.5 x ULN
Serum Chemistry	Gamma-Glutamyl Transferase (GGT)	> 3 x ULN
Serum Chemistry	Lactate Dehydrogenase (LDH)	> 3 x ULN
Serum Chemistry	Total Bilirubin	> 2 x ULN
Hematology	White Blood Cell Count	≤ 2.8 10^9/L
Hematology	Absolute Neutrophils Count	< 1.5 10^9/L

Frequency distributions of the clinical laboratory tests of interest listed above will summarized for potentially clinically significant (PCS) values at individual analysis visits and any post-baseline visit.

eDISH (evaluation of Drug-Induced Serious Hepatotoxicity)^[26] plots will be created for the following highest post-baseline laboratory test values versus highest post-baseline total bilirubin values:

- Alkaline Phosphatase (ALP) versus Total Bilirubin
- Alanine Aminotransferase (ALT) versus Total Bilirubin
- Aspartate Aminotransferase (AST) versus Total Bilirubin

The peak post-baseline ALP, ALT, AST, and total bilirubin values will each be divided by their respective upper limit of normal (ULN) range. Those individual ALP, ALT, and AST transformed values will be plotted against transformed total bilirubin values to help identify the following [27]:

- Hy's Law Range: ALP, ALT, or AST > 3 x ULN and Total Bilirubin > 2 x ULN
- Hyperbilirubinemia: ALP, ALT, or AST ≤ 3 x ULN and Total Bilirubin ≥ 2 x ULN
- Temple's Corollary Range: ALP, ALT, or AST > 3 x ULN and Total Bilirubin ≤ 2 x ULN

The following additional laboratory tests collected will be provided in subject listings only:

- Urine Pregnancy Tests
 - o All women of childbearing potential
- Serology Tests:
 - o HIV, Hepatitis B Virus Surface Antigen, and Hepatitis C Virus Antibody Tests
 - o If the screening hepatitis C antibody test result is reactive, a nucleic acid test for HCV RNA should be performed for confirmation of chronic infection.
 - o If the screening HIV test is positive, a confirmatory Western Blot test should be performed to confirm HIV status.
- Urine Drug Screen Tests
 - o Cannabinoids, Opioids, and Benzodiazepines
- Alcohol Breathalyzer Screen Tests

The clinical laboratory test results will be listed and accompanied by normal ranges when provided; values outside the normal ranges will be flagged. All abnormal clinical laboratory test results for hematology, serum chemistry, and urinalysis will be provided in a subject listing. In the event any clinical laboratory samples were collected more than once with different requisition numbers within the same date and time, the most abnormal results followed by the greatest change from baseline will used in the summary tables. All samples will be reported in the subject listings and these will be documented in the SDTM Study Data Reviewer's Guide.

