7 SELECTION AND WITHDRAWAL OF SUBJECTS

7.1 Subject Inclusion Criteria

Inclusion Criteria: Screening

- 1. An IRB-approved written informed consent and privacy language (Health Insurance Portability and Accountability Act) authorization must be obtained from the subject prior to performing any study-related procedures.
- 2. Subjects who consent to being included in a subject registry database.
- 3. Male and female subjects \geq 18 and \leq 75 years of age.
- 4. Subjects with a diagnosis of Type 2 diabetes.
- 5. Subjects with a score of ≥4 and ≤9 on the 11-point NRS for average pain intensity over the past 24 hours at Visit 1.
- 6. Hemoglobin A1c (HbA1c) ≤11% (measured at Visit 1).
- 7. Stable use of diabetic medications beginning 1 month prior to Visit 1. (Adequate glycemic control with only diet and exercise is also permitted).
- 8. Subjects with diabetic peripheral neuropathy, of symmetrical nature and in lower extremities for ≥6 months to ≤10 years, and diagnosed by a score of ≥3 on the Michigan Neuropathy Screening Instrument.
- 9. Body mass index $<40 \text{ kg/m}^2$.
- 10. Calculated creatinine clearance ≥60 mL/minute (Cockcroft-Gault formula).
- 11. Clinical laboratory values must be within normal limits or deemed not clinically significant by the investigator and sponsor-designated medical monitor.
- 12. Female subjects must either:
- Be of non-childbearing potential:
 - Post-menopausal (defined as at least 1 year without any menses) prior to Visit 1;
 or
 - Documented as surgically sterile.
- Or, if of childbearing potential:
 - Agree not to try to become pregnant during the study and for 28 days after the final administration of investigational product;
 - o Have a negative urine pregnancy test at Visit 1; and
 - o If heterosexually active, agree to consistently use 2 forms of highly effective birth control (at least 1 of which must be a barrier method) starting at Visit 1 and continuing throughout the study period and for 28 days after the final administration of investigational product.

- 13. Female subjects must agree not to breastfeed starting at Visit 1 and continuing throughout the study period and for 28 days after the final administration of investigational product.
- 14. Female subjects must not donate ova starting at Visit 1 and continuing throughout the study period and for 28 days after the final administration of investigational product.

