5.1.4 Baseline and Post-Baseline Values

Unless otherwise specified, the baseline value is defined as the last measurement/assessment collected/derived on Day 1 or screening. Unless otherwise specified, post-baseline values are defined as collected/derived measurements/assessments after Day 1.

For specific questionnaire assessments, missing responses on Day 1 will not be substituted for screening values for the baseline specific questionnaires. If the total score cannot be calculated at Day 1, then the screening visit will be used if the total score can be calculated at screening. If the total score cannot be calculated for both screening and Day 1 visits, then the latest individual values and subscale scores will be used for the baseline. All questions within a specific questionnaire will be paired together in an analysis visit for the baseline records.

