10.3 Vital Sign Measurements

Systolic blood pressure (mmHg), diastolic blood pressure (mmHg), and pulse rate (bpm) will be assessed at analysis visits Screening, Baseline, Week 2, Week 4, and Last Post-Baseline Visit. Observed vital signs and changes from baseline will be summarized for the vital signs using descriptive statistics.

10.4 12-Lead Electrocardiogram (ECG)

Electrocardiogram (ECG) parameters will be measured at Screening, Baseline, and Week 4/Early Termination. Descriptive statistics of observed values and changes from baseline will be summarized for:

- ECG Mean Heart Rate (beats/min)
- RR Interval (msec)
- PR Interval (msec)
- QRS Duration (msec)
- OTcF Interval (msec)

QT Interval and QTcB Interval will be collected and provided in subject listings, but not included in the summary tables. The interpretation of 'Normal', 'Abnormal, not clinically significant', and 'Abnormal, clinically significant' will be summarized at each analysis visit. A shift table of these interpretations will be provided from baseline to Week 4 and Last Post-Baseline Visit.

Frequency distributions of the QTcF Interval will be displayed for abnormally high values that are greater than their baseline value at any post-baseline visit and the following data cuts:

- > 450 msec and > Baseline Value
- > 470 msec and > Baseline Value
- > 500 msec and > Baseline Value

Additionally, the change from baseline frequency distributions of the QTcF Interval will displayed for the following data cuts:

- > 30 msec
- > 60 msec

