14.3.5.1.1.2	Safety	Table: Shifts from Baseline Clinical Laboratory Results for Hematology			
14.3.5.1.2.1	Safety	Table: Change from Baseline Clinical Laboratory Results for Serum Chemistry (Liver Function Tests)			
14.3.5.1.2.2	Safety	Table: Change from Baseline Clinical Laboratory Results for Serum Chemistry (Non-Liver Function Tests)			
14.3.5.1.2.3	Safety	Table: Shifts from Baseline Clinical Laboratory Results for Serum Chemistry (Liver Function Tests)			
14.3.5.1.2.4	Safety	Table: Shifts from Baseline Clinical Laboratory Results for Serum Chemistry (Non-Liver Function Tests)			
14.3.5.1.3.1	Safety	Table: Change from Baseline Clinical Laboratory Results for Urinalysis (Numeric Data)			
14.3.5.1.3.2	Safety	Table: Frequency Distributions for Clinical Laboratory Results for Urinalysis (Categorical Data)			
14.3.5.1.3.3	Safety	Table: Shifts from Baseline Clinical Laboratory Results for Urinalysis (Numeric Data)			
14.3.5.1.3.4	Safety	Table: Shifts from Baseline Clinical Laboratory Results for Urinalysis (Categorical Data)			
14.3.5.1.4	Safety*	Table: Potentially Clinically Significant Clinical Laboratory Results			
14.3.5.1.5	Safety*	Figure: eDISH Plots of Clinical Laboratory Results versus Total Bilirubin			
14.3.5.2	Safety	Table: Change from Baseline Vital Sign Measurements			
14.3.5.3.1	Safety	Table: Change from Baseline Electrocardiogram Parameter Results			

Number	Population*	TFL: Title
14.3.5.3.2	Safety	Table: Frequency Distributions for Electrocardiogram Interpretations
14.3.5.3.3	Safety	Table: Shifts from Baseline Electrocardiogram Interpretations
14.3.5.3.4	Safety*	Table: Frequency Distributions for Abnormally High QTcF Interval Results
14.3.5.4	Safety	Table: Study Drug Treatment Compliance and Exposure
14.3.5.5	Safety	Table: Rescue Medication
14.3.5.6.1	Safety	Table: Concomitant Medications by ATC Class and Preferred Term
14.3.5.6.2	Safety	Table: Concomitant Analgesic Medications by ATC Class and Preferred Term
14.3.5.7	Safety	Listing: Change to Abnormal Post-Baseline Physical Examinations
14.3.5.8.1	Safety	Table: Change from Baseline Sheehan Suicidality Tracking Scale
14.3.5.8.2	Safety	Table: Frequency Distributions for Abnormal Post-Baseline Sheehan Suicidality Tracking Scale Results
14.3.5.8.3	Safety	Listing: Abnormal Post-Baseline Sheehan Suicidality Tracking Scale Results
14.3.5.9	Safety	Table: Body Weight (kg)
14.3.5.10	Safety	Table: Major Protocol Deviations

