^{*} Denotes a table that will be provided in the topline analyses after database lock.

14.List of Planned CSR Appendices in Section 16.2

The following are planned appendix listings used to support the CSR in Section 16.2. All subjects will be provided regardless of their randomized/treated status. The same details mentioned in the planned TFL's in Section 13 will be applied to the planned appendices.

Number	Appendix Title		

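### Post-baseline PCS laboratory counts include subjects already beyond the limit before dosing, mainly for BUN, GGT, LDH, WBC, neutrophils and the ULN branch of creatinine

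*SAP*

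**What the plan says.** SAP 10.2 sets limits for ten laboratory tests and asks for frequency counts of "potentially clinically significant (PCS) values at individual analysis visits and any post-baseline visit". Nine limits are fixed, either a multiple of the ULN or an absolute cell count. Creatinine alone refers to baseline, as one branch of an either/or rule: ">1.5 x Baseline or > 1.5 x ULN".

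The output appears in the SAP Section 13 list as 14.3.5.1.4, "Table: Potentially Clinically Significant Clinical Laboratory Results", and carries the asterisk whose footnote reads "Denotes a table that will be provided in the topline analyses after database lock".

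Three other parts of the SAP bear on it:
- SAP 5.1.4: "the baseline value is defined as the last measurement/assessment collected/derived on Day 1 or screening". Each subject's pre-dose status is therefore available to a program.
- SAP 10.4: QTcF counts are restricted to "abnormally high values that are greater than their baseline value at any post-baseline visit".
- SAP 10.2, shift tables: the categories are "Numeric Results: Low, Normal, and High", which refer to the normal range and not to the PCS limits.

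On entry, Protocol 7.1 says "Clinical laboratory values must be within normal limits or deemed not clinically significant", judged by both the investigator and the medical monitor. It also requires creatinine clearance of at least 60 mL/min. Exclusion 6 in Protocol 7.2 bars raised ALT, AST, ALP and bilirubin at screening, without waivers.

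**The concern.** Suppose a subject has GGT at 4 x ULN on Day 1 and 4 x ULN at Week 4. Nothing has happened on treatment, yet the subject meets the limit after baseline and is counted. With about 75 subjects per arm and rare abnormalities, a few such subjects falling by chance into one arm can look like a dose signal, or can mask a real one.

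The SAP treats pre-dose findings differently elsewhere. QTcF must exceed both the threshold and the subject's own baseline. Under SAP 10.1, Day 1 adverse events arising from laboratory samples taken before dispensing are not treatment-emergent. The same pre-dose value can thus be kept out of the adverse event tables and still enter the PCS count.

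The shift tables do not fill the gap. A High-to-High entry for GGT could be 1.2 rising to 4 x ULN (a new PCS value) or 4 staying at 4 x ULN (an old one). They are also not marked for topline.

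**Working it through.** **Which tests are exposed.** Entry rules set against PCS limits:

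| Test | PCS limit | Can it be at PCS level at screening? |
|---|---|---|
| ALT, AST | > 3 x ULN | No; 1.5 x ULN or more is excluded |
| ALP | > 2 x ULN | No; 1.5 x ULN or more is excluded |
| Total bilirubin | > 2 x ULN | No; excluded whether the criterion is read as any abnormal value or as 1.5 x ULN or more |
| Creatinine | > 1.5 x baseline, or > 1.5 x ULN | First branch: no, by construction. Second: limited, not barred |
| BUN, GGT, LDH, WBC, neutrophils | fixed | Yes, if judged not clinically significant |

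For the first four tests, only a rise between screening and Day 1 could create a pre-existing case. That is possible because Protocol 10.2 draws the Day 1 blood from subjects already randomized.

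For creatinine, the Cockcroft-Gault ceiling for a man of 60 years and 100 kg at 60 mL/min is (140 − 60) × 100 / (72 × 60) = 1.85 mg/dL. This exceeds 1.5 x ULN only if the ULN is below 1.85 / 1.5 = 1.23 mg/dL. The laboratory's ULN is not given.

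**Size of the chance imbalance.** The PCS section states no figure to reproduce. The inputs are:
- n = 75 per arm, four arms, 1:1:1:1 (SAP 4.2, 4.3).
- q, the proportion of subjects already beyond the limit on a given test. It is not in the documents and is assumed here from 0.5% to 5%.
- Persistence: every such subject is still beyond the limit after baseline. This is an assumption. For the exposed tests it concerns one scheduled sample (Week 4 or early termination), because Week 2 and Week 5 samples are for liver tests only. If only a fraction r persists, read the result at q × r; for example, q = 2% with half persisting gives the 1% row.

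Let X be the count in one arm, X ~ Binomial(75, q), with f its probability function and F its cumulative function. The chance that at least one of three dose arms exceeds placebo by 3 or more is

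P = Σx f(x) × [1 − F(x + 2)³].

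At q = 1%: f(0) = 0.4706, f(1) = 0.3565, f(2) = 0.1332; F(2) = 0.9603, F(3) = 0.9931, F(4) = 0.9990.
- x = 0: 0.4706 × (1 − 0.9603³) = 0.0538
- x = 1: 0.3565 × (1 − 0.9931³) = 0.0073
- x = 2: 0.1332 × (1 − 0.9990³) = 0.0004
- Sum, later terms negligible, unrounded terms carried: 0.0616, or 6.2%.

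For the 200 mg arm alone, replace the bracket by 1 − F(x + 2).

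| Assumed q | Expected per arm | Any dose arm 3 or more above placebo | 200 mg arm 3 or more above placebo |
|---|---|---|---|
| 0.5% | 0.375 | 1.4% | 0.5% |
| 1% | 0.75 | 6.2% | 2.1% |
| 2% | 1.5 | 17.8% | 6.8% |
| 3% | 2.25 | 26.3% | 11.1% |
| 5% | 3.75 | 36.3% | 17.1% |

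For the six exposed tests taken as independent, the chance of such an excess on at least one is 1 − (1 − 0.0616)⁶ = 31.7% at q = 1% each, and 7.9% at 0.5%. Independence is a simplification: WBC and neutrophils overlap, and so may BUN and creatinine.

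**After the change.** In a row restricted to subjects not beyond the limit at baseline, pre-existing cases contribute zero in every arm at any q.

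**The case against.** The strongest reply is that the table may already show what is needed. The PCS sentence covers individual analysis visits as well as the any-post-baseline count. SAP 10.2 lists Screening and Baseline among its analysis visits, and elsewhere in that section adds the word post-baseline when it means only later visits. On that reading, pre-dose counts by arm stand beside the post-baseline ones. Listing 14.3.4 of abnormal results is also topline, so with few cases a reader can trace each subject.

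Much of this stands. The natural reading probably includes Baseline, although the SAP does not say so and the mock shells are a separate document. But counts by visit are marginal: three subjects at Baseline and three after it need not be the same three. The listing allows a check by hand but does not change the table.

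A second objection also stands. Removing every baseline-PCS subject from the only headline count could hide real worsening. A subject whose GGT rises from 3.1 to 10 x ULN would disappear from it. The QTcF rule keeps such a subject, because it asks only that the value exceed baseline. The existing counts should therefore stay.

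Third, two parties must clear any out-of-range value at entry, so pre-dose PCS values may be rare. At 0.5% prevalence the figure is only 1.4%.

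**Conclusion.** The point holds in a limited form. As written, the any-post-baseline PCS count in a topline table mixes new values with values present before dosing, and no planned summary table separates them subject by subject. The chance that this alone puts some dose arm 3 or more subjects above placebo on one test runs from 1.4% to 36.3% as the assumed prevalence runs from 0.5% to 5%. It rests on that assumption, on full persistence, and on taking the worst of three arms.

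A reader might infer more, but the documents do not support it:
- That all ten tests are affected. Four are barred from PCS level at screening, and one branch of creatinine cannot be met at baseline.
- That the comparison is biased. Under randomization, pre-existing cases are equal across arms in expectation; they add noise.
- That a false positive test could follow. SAP 5.3.4 rules out formal testing of safety data, and the safety objective (Protocol 5.2, SAP 3.2) concerns multiple dose levels without naming placebo as comparator. The risk is misreading small counts.
- That pre-dose values are concealed. Baseline counts may be shown, and the abnormal-results listing is topline.

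This is a low-severity improvement to a descriptive table.

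**What to change.** In SAP 10.2 and the shell for Table 14.3.5.1.4:
1. Keep the current counts.
2. For each test, add a treatment-emergent row. Numerator: subjects beyond the limit after baseline and not at baseline. Denominator: subjects not beyond the limit at baseline who have a post-baseline value.
3. Add a row for subjects beyond the limit at baseline, showing how many worsened from their own baseline, in the spirit of the QTcF rule. For WBC and neutrophils, worse means lower.
4. For creatinine, apply the baseline condition only to the branch above 1.5 x ULN, and count any value above 1.5 x baseline as emergent. The two branches then have different denominators, so show them on separate lines.
5. State that Baseline counts are shown.

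The cost is one programming condition, a few extra rows, and slightly smaller denominators in the new row. No new data are needed, because SAP 5.1.4 already defines baseline.

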In summary, NYX-2925 has been sufficiently tested in preclinical studies for safety and tolerability over a wide dose range, with exposures greater than the proposed clinical doses. General toxicology studies support clinical studies up to and including 6 weeks of daily doses. Results from the first-in-human study indicate that NYX-2925 is safe and well-tolerated in the male and female healthy volunteers dosed to date at single doses up to 1200 mg, and multiple doses up to 900 mg given daily for 7 days. The preclinical and phase 1 clinical data support further testing in humans.

In addition to the current trial, there are 2 other ongoing clinical studies with NYX-2925. NYX-2925-1003 is a phase 1, double-blind, placebo-controlled, pilot, crossover study to assess the effects of NYX-2925 on sleep architecture as assessed by polysomnography in healthy male subjects aged 40-55 when their bedtime is advanced by 3 hours in a sleep laboratory. Also ongoing is study NYX-2925-2002, in subjects with fibromyalgia. The primary objective of this study is to determine whether NYX-2925 modulates central nervous system activity in key pain neural circuitry, consistent with the potential to provide analgesia in subjects with fibromyalgia, as assessed by neuroimaging methods. Secondarily, this study will provide a preliminary characterization of the safety of NYX-2925 in subjects with fibromyalgia.

Further, there is planned study; a phase 1, double-blind, randomized, sponsor-open, parallel, placebo-controlled exploratory study to assess the effect of multiple dose levels of NYX-2925 on

the brain function of healthy volunteers as measured by electroencephalogram and event related potentials.

To date, one serious adverse event, cholelithiasis requiring inpatient hospitalization, has been reported in the clinical development program for NYX-2925, that being in the current study, NYX-2925-2001. The event is considered not related to NYX-2925.

This study (NYX-2925-2001) is a randomized, double-blind, placebo-controlled, multiple-dose study to assess the efficacy and safety of NYX-2925 in subjects with neuropathic pain associated with diabetic peripheral neuropathy. NYX-2925 will be provided as capsules for oral administration.

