11 STOPPING CRITERIA

Subjects will be withdrawn from the treatment period of the study if any of the following criteria are met. Repeat testing must be completed within 48-72 hours:

Repeated results (i.e. values confirmed by repeat testing):

- Serum total bilirubin $\geq 2.5 \text{ mg/dL}$, or
- Subject meets one of the following criteria
 - ALT or AST >3 x ULN, or
 - ALT or AST \geq 3 x ULN, and total bilirubin \geq 2 x ULN, or
 - ALT or AST \geq 3 x ULN, with the appearance of fatigue, nausea, vomiting, right upper quadrant pain, or tenderness, fever, rash, or eosinophilia (>5%), or
 - Alkaline phosphatase $\geq 2x$ ULN.

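### The eDISH range labels in SAP 10.2 put alkaline phosphatase on the same footing as ALT and AST, so an ALP rise alone can be labelled Hy's Law range

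*SAP*

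**What the plan says.** SAP 10.2 divides each subject's highest post-baseline ALP, ALT, AST and total bilirubin by the upper limit of normal. It plans three plots, one per enzyme, and the ALP plot is listed in its own right: "Alkaline Phosphatase (ALP) versus Total Bilirubin". The purpose is given as "Those individual ALP, ALT, and AST transformed values will be plotted against transformed total bilirubin values to help identify the following", and three ranges are then defined. The first reads "Hy's Law Range: ALP, ALT, or AST > 3 x ULN and Total Bilirubin > 2 x ULN". The second, named Hyperbilirubinemia, takes any of the same three enzymes when it is no higher than 3 x ULN while bilirubin is at least 2 x ULN. The third reads "Temple's Corollary Range: ALP, ALT, or AST > 3 x ULN and Total Bilirubin ≤ 2 x ULN".

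The plots are figure 14.3.5.1.5 in SAP Section 13, on the Safety population, with the asterisk that marks topline output.

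Two other places group the enzymes differently. The PCS table in SAP 10.2 flags ALP above 2 x ULN and ALT or AST above 3 x ULN. Protocol Section 11 has a combined enzyme-and-bilirubin criterion ("3 x ULN, and total bilirubin" at or above 2 x ULN) that names only ALT or AST. ALP stands there as a separate criterion at 2 x ULN or more, with no bilirubin condition. SAP 4.7, which lists changes from the protocol, does not mention the different grouping.

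**The concern.** The ranges treat the three enzymes as interchangeable, although elsewhere the trial's documents keep ALP apart. The SAP presents these plots as an evaluation of serious drug-induced liver injury, so a point in the Hy's Law range will be read as a serious liver signal. If ALP alone can put a subject there, the label no longer says that a transaminase was raised together with bilirubin, which is the only enzyme-and-bilirubin pairing the protocol recognises. The same applies to Temple's Corollary when only ALP is high. The figure is among the first safety outputs to be seen, so the labels should be settled before database lock.

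**Working it through.** The documents give no figure to reproduce, so the check applies the written rules to example subjects.

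**Inputs.** For a plotted enzyme peak E and bilirubin peak B, both in multiples of ULN, SAP 10.2 gives:

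- Hy's Law: E > 3 and B > 2
- Hyperbilirubinemia: E ≤ 3 and B ≥ 2
- Temple's Corollary: E > 3 and B ≤ 2

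The enzyme criteria of protocol Section 11 are: ALT or AST > 3; ALT or AST ≥ 3 with bilirubin ≥ 2; ALT or AST ≥ 3 with listed symptoms or eosinophilia; ALP ≥ 2. The symptom criterion is left out because the examples carry no symptoms. The separate bilirubin limit of 2.5 mg/dL is left out because it depends on a laboratory ULN that is not given.

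**Results.** The values are assumed for illustration and are not trial data.

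| ALP / ALT / AST / bilirubin (x ULN) | ALP plot | ALT plot | AST plot | Section 11 enzyme criteria met |
|---|---|---|---|---|
| 3.5 / 2 / 2 / 2.5 | Hy's Law | Hyperbilirubinemia | Hyperbilirubinemia | ALP only |
| 4 / 1 / 1 / 1 | Temple's | none | none | ALP only |
| 2.5 / 1 / 1 / 3 | Hyperbilirubinemia | Hyperbilirubinemia | Hyperbilirubinemia | ALP only |
| 1 / 4 / 4 / 3 | Hyperbilirubinemia | Hy's Law | Hy's Law | ALT/AST; ALT/AST with bilirubin |
| 4 / 4 / 1 / 3 | Hy's Law | Hy's Law | Hyperbilirubinemia | ALT/AST; ALT/AST with bilirubin; ALP |
| 1 / 4 / 1 / 1 | none | Temple's | none | ALT/AST |

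Row 1: on the ALP plot 3.5 > 3 and 2.5 > 2, so the label is Hy's Law. On the ALT and AST plots 2 ≤ 3 and 2.5 ≥ 2, so the label is Hyperbilirubinemia. The protocol's combined criterion fails because 2 < 3.

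Row 2: an isolated ALP rise takes the Temple's label, because 4 > 3 and 1 ≤ 2.

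Row 3 shows the reverse mismatch. An ALP of 2.5 is above the SAP's own PCS cut and the protocol's ALP limit, yet no ALP finding shows on the plot, because its cut is 3.

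**Reading the rules as composites.** If the three enzymes joined by *or* are taken as one rule per subject, row 4 is both Hy's Law (through ALT) and Hyperbilirubinemia (through ALP). The ranges then overlap, so the plot-by-plot reading is the workable one. The ALP problem appears under both readings.

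**After limiting the labels to ALT or AST.** Row 1 is Hyperbilirubinemia only. Row 2 has no range label. Rows 4, 5 and 6 keep their Hy's Law and Temple's labels on the ALT and AST plots. No subject with ALT or AST above 3 x ULN loses a label on those plots.

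**The case against.** The case against acting has several parts, and much of it stands.

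*The enzymes are plotted separately.* A point on the ALP plot is visibly an ALP point, and the row 1 subject is Hyperbilirubinemia on the ALT and AST plots. The enzyme list could be shorthand for whichever enzyme is on the axis. That is true, but on this reading the ALP plot still carries the Hy's Law and Temple's labels.

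*No count is planned.* SAP Section 13 lists a figure and no table of Hy's Law cases. A reader might infer that one ALP-driven case would move a reported rate from 0/225 to 1/225 on active drug (3 x 75 = 225). The SAP produces no such rate.

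*Other outputs separate the enzymes.* The PCS table (14.3.5.1.4) and the abnormal laboratory listing (14.3.4), both topline, and the chemistry listing (16.2.8.2) let a reader see whether ALP or ALT/AST rose. This stands, and it is why a reader should not infer that the overall hepatic safety conclusion would be misstated.

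*Section 11 is not a reporting rule.* It sets withdrawal criteria on values confirmed by repeat testing, whereas the plots show peak values without a confirmation requirement. The protocol names neither Hy's Law nor Temple's Corollary. This is therefore an inconsistency in how ALP is grouped and not a breach of a reporting requirement. The absence from SAP 4.7 should be read in the same light.

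*The clinical premise is external.* Neither document says that Hy's Law should isolate hepatocellular injury, and the guidance that the SAP cites for the ranges was not available. The point rests only on the mismatch between sections.

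*The cholelithiasis event.* The protocol Introduction reports "one serious adverse event, cholelithiasis requiring inpatient hospitalization", in this study and considered unrelated. It gives no ALP or bilirubin values. It shows that a biliary event can occur in this population, but nothing about how often the label would be triggered.

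*The comparison signs.* The SAP uses strict inequalities where the protocol's combined criterion uses at-least signs. A reader might want these aligned, but the difference matters only exactly at a limit, and Section 11 as it reads here uses both forms for ALT/AST. Changing only the Hy's Law rule would make the ranges overlap: ALT 3 with bilirubin 2 would also be Hyperbilirubinemia, and ALT 4 with bilirubin 2 would also be Temple's.

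**Conclusion.** The point holds as a labelling error in SAP 10.2. Followed exactly, the plan gives the Hy's Law or Temple's label to a subject whose only enzyme above 3 x ULN is ALP. That disagrees with how protocol Section 11 and the SAP's own PCS table group ALP.

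The size is limited: a misleading label on one plot of a topline figure, and in any text that repeats it. Safety analysis is descriptive, no test or count depends on the label, and no ALT or AST case is hidden. How many subjects would be affected cannot be known from the documents.

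The conclusion rests on the written ranges and on the assumed example values. It needs no outside definition of Hy's Law. It merits correction because the remedy is nearly free and the label carries weight with safety readers.

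**What to change.** In SAP 10.2, remove ALP from the definitions of all three labelled ranges, so that they apply only to the ALT and AST plots. Keep ALP against bilirubin as a separate plot without those labels. If it has an ALP reference line, place it at the PCS cut of 2 x ULN.

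Leave the inequality signs as they are. If the sponsor prefers to align them with Section 11, rewrite all three ranges together so that they stay mutually exclusive.

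The cost is a few lines of SAP text and the annotation of figure 14.3.5.1.5. No new data, extra analysis or change to the stopping criteria is involved.
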